3.5 Dose Modifications

All toxicity grades below are described using the NCI Common Terminology Criteria for Adverse Events (CTCAE) version 5.0.

All appropriate treatment areas should have access to a copy of the CTCAE version 5.0. A copy of the CTCAE version 5.0 can be downloaded from the CTEP website

(http://ctep.cancer.gov/protocolDevelopment/electronic_applications/ctc.htm).

The side effects observed with copanlisib (BAY 80-6946) are consistent with those observed with other PI3K inhibitors.

Copanlisib will be administered at fixed dose (60 mg) intravenously on Days 1, 8, and 15 on a 28-Day cycle. Copanlisib dose reduction instructions provided in **Table 1** serve as guidelines to allow ongoing treatment for patients without signs or symptoms of progression while monitoring patient safety. If there is need to interrupt dosing for grade 3/4 toxicity, then there will be a dose reduction as per the table below, once toxicity improves to grade 1 or baseline. Selected toxicities / adverse events of interest for copanlisib include hyperglycemia, rash, hypertension, diarrhea.

Table 1 Overall Dose Modification Guideline for Copanlisib (BAY 80-6946)-Related Adverse Events

	Copanlisib
Starting dose	60 mg
First reduction	45 mg
Second reduction	30 mg

Dose may be suspended for up to 4 weeks due to toxicity. Patients requiring treatment to be held for >4 weeks will be taken off treatment. If treatment held for laboratory abnormality, recheck labs in one week. No dose reduction is allowed for patients treated at a dose 30 mg of copanlisib – if there is an indication for further dose reduction, the patient must permanently discontinue copanlisib. Dose re-escalation is not allowed after a dose reduction.

Rev. Add16

Dose Modification rules for transient post-infusion hyperglycemia

Patients who develop post-infusion glucose increases of grade 2 after study drug administration may continue treatment. However, the next infusion must be delayed until the patient's pre-infusion glucose levels return to < 160 mg/dL (fasting) or < 200 mg/dL (non-fasting). Guidelines for the management of transient glucose increases are given in [Appendix III](#). Continuing occurrence of post-infusion blood glucose increases of grade ≥ 3 despite optimal glucose lowering therapy after 2 infusions of copanlisib, will require dose reduction by one dose level.

- Further dose reduction (**where appropriate per study design/population**) is allowed as long as discontinuation criteria was not met.
- Dose re-escalation is allowed when a patient has achieved controlled glucose levels per investigator's judgment.
- Occurrence of post-infusion non-life threatening hyperglycemia requiring interventions at the protocol defined lowest dose level despite optimal

glucose lowering therapy (after at least one cycle of treatment) requires permanent discontinuation of the study drug.

- Occurrence of post infusion life-threatening copanlisib related hyperglycemia requires permanent discontinuation of the study drug

Management of Hyperglycemia

Metformin is the first antihyperglycemic medication of choice because of the lower risk of hypoglycemia with this agent. Because metformin in some patients may also cause diarrhea and can be poorly tolerated, other antihyperglycemic medications such as sulfonylureas (e.g. glimepiride, glipizide) can be used. Extra caution should be used with other drugs such as sulfonylureas because of the increased risk for hypoglycemia with these agents. Consultation with an endocrinologist can be helpful in managing hyperglycemia.

Insulin should only be used for patients with persistent, symptomatic hyperglycemia. It should not be used to lower glucose level on the day of infusion due to the risk of hypoglycemia. On treatment days, it is best to hydrate the patient and not give insulin to reduce glucose levels to meet study treatment criteria.

Management guidelines for fasting patients with hyperglycemia are listed below in Table 2.

Table 2: Management of Hyperglycemia

Grade	Intervention	Dose Adjustment
1	Initiation of an oral anti-hyperglycemic agent (e.g., metformin) and additional glucose monitoring should be considered.	No change.
2	Initiation or increased dose of an oral anti-hyperglycemic agent (e.g., metformin) and additional glucose monitoring should be considered.	Dosing with copanlisib may either be held or continued per Investigator evaluation.
3, asymptomatic	Patient should be managed as per standard care, including implementation of additional glucose monitoring and initiation and/or increase of anti-hyperglycemic therapy (e.g., metformin).	Consideration should be given to suspend copanlisib dosing until the hyperglycemia resolves to Grade \leq 2. Dosing with copanlisib may resume at the same dose level or at one dose level lower as outlined in Table 1 and after discussion with the Study Principal Investigator.
3, symptomatic (e.g., blurred vision, frequent urination, excessive thirst) or grade 4	Patient should be managed as per standard care, including implementation of additional glucose monitoring and initiation and/or increase of anti-hyperglycemic therapy	Copanlisib dosing should be suspended until the hyperglycemia resolves to Grade \leq 2. The patient will be discontinued from the study if such therapy fails to control their hyperglycemia. Dosing with copanlisib may otherwise resume at one dose level lower as outlined in Table 1.

*Based on fasting glucose level

Management of Rash

Treatment related rash has been reported with copanlisib. While most were CTCAE v3.0 Grade 1 or Grade 2 in severity, few patients experienced Grade 3 rash. Rash is generally macular or maculo-papular with or without pruritus, with some having developed desquamation. Patients with severe rash should be monitored for associated signs and symptoms, such as fever and hypotension that may be suggestive of a systemic hypersensitivity reaction. For severe rash, hold all study treatment until Grade ≤ 1 (see Table 3 below), and patients should be treated with supportive therapy per standard of care. Use of topical antihistamine, as well as topical or systemic corticosteroids, may be considered. There is no evidence for a phototoxic potential of copanlisib.

Table 3: Dose Delay and Modification Guidelines for Rash

Grade	Intervention	Dose Adjustment
Grade 1	Consider prescribing topical corticosteroids ^a	Continue dosing at current dose and monitor for change in severity.
Grade 2	Consider treatment with supportive therapy (e.g., topical or oral corticosteroids ^{a, b}).	Consider holding copanlisib or reducing to the next lower dose if rash is troublesome.
Grade 3 or 4	Consider treatment with supportive therapy (e.g., topical or oral corticosteroids ^{a, b}). Consider dermatological consultation. Consider obtaining photographs of rash if permitted by local regulations.	Hold all study treatment until Grade ≤ 1 . For Grade 3, restart copanlisib at the next lower dose upon discussion with Overall Principal Investigator, or permanently discontinue treatment. For Grade 4, permanently discontinue treatment.

a Suggested topical steroids include, hydrocortisone 2.5% to face twice daily, triamcinolone 0.1% or fluocinonide 0.1% cream to body bid.

b Suggested oral steroids include methylprednisolone dose pack or prednisone 60 mg daily followed by a taper (e.g., 60 mg \times 2 days, 40 mg \times 2 days, 20 mg \times 2 days, etc.).

Management of Hypertension

Patients receiving copanlisib who have experienced hypertension and blood pressure should be monitored at each visit. In subjects with an initial BP reading within the hypertensive range, a second reading should be taken at least 2 minutes later, with the two readings averaged to obtain a final BP measurement.

For patients who develop HTN or worsening HTN during study treatment, antihypertensive medication should be initiated or optimized to achieve target blood pressure before interruption or dose reduction of the study treatment at the discretion of the investigator. If hypertension is persistent despite adequate anti-HTN therapy including titration of anti-HTN medication or introduction of additional anti-HTN medications, dose interruption, reduction or discontinuation is recommended. If Grade 4 HTN develops, permanently discontinue treatment. Patients with prior history of hypertension (on anti-hypertensive agents) should monitor/record their BP at home while on copanlisib.

It is important that patients with pre-existing arterial hypertension adhere to their regular medication schedule and take their usual doses on the days of study drug infusion.

The management of acute blood pressure (BP) increases following copanlisib will need to be individualized for each patient, but experience from a Bayer-sponsored phase 1 study with copanlisib has suggested the benefit of dihydropyridine calcium channel blockers (*i.e.*, amlodipine, felodipine). Nitrates should also be considered. Verapamil and diltiazem (non-dihydropyridine calcium channel blockers and moderate inhibitors of CYP3A4) should be used with caution due to a potential CYP3A4 interaction. In general, it is advisable for sites to be prepared, so that anti-hypertensive medication is readily available in case of need.

In the event of the occurrence of arterial hypertension $\geq 150/90$ mmHg during infusion of copanlisib at any cycle, antihypertensive treatment is suggested as indicated in [Appendix IV](#). In the event of the occurrence of grade 3 arterial hypertension ($\geq 160/100$ mmHg) during infusion of copanlisib, the infusion should be interrupted and anti-hypertensive treatment as suggested above is administered. Infusion can be resumed when BP has returned to $< 150/90$ mmHg.

Rev. Add16

Blood pressure measurement on treatment days

Blood pressure will be measured prior to each copanlisib dose (no more than 4 measurements) until there are two consecutive results $< 150/90$ mmHg with at least a 15 min interval between the measurements to be able to start the infusion of the study medication (pre-dose). The investigator can consider a medical intervention to maintain blood pressure in values appropriate for infusion. The investigator must delay the infusion until blood pressure values are below 150/90.

On copanlisib infusion days, blood pressure will be measured at pre dose, 30 min after the start of infusion, right after the end of infusion; and 1 h and 2 h after the end of copanlisib infusion.

NOTE: Time window of ± 10 min is allowed for all post dose blood pressure measurements.

Event	Management Guideline	Dose Modification	
Definitions used in the table:			
	
 - Persistent hypertension: Hypertension detected in two separate readings during up to three subsequent visits. - Well-controlled hypertension: Blood pressure of SBP \leq 150 mmHg and DBP \leq 90 mmHg in two separate readings during up to three subsequent visits. - Symptomatic hypertension: Hypertension associated with symptoms (e.g., headache, light-headedness, vertigo, tinnitus, episodes of fainting) that resolve after the blood pressure is controlled within the normal range. - Asymptomatic hypertension: SBP $>$ 150 mmHg and/or DBP $>$ 90 mmHg in the absence of the above symptoms. 		
(Scenario A)	
 • Asymptomatic and persistent SBP of \geq 150 and $<$ 160 mmHg, or DBP \geq 90 and $<$ 100 mmHg, OR • Clinically significant increase in DBP of 20 mmHg (but still below 100 mmHg). 	
 • Adjust current or initiate new antihypertensive medication(s). • Titrate antihypertensive medication(s) during the next 2 weeks to achieve well-controlled BP. If BP is not well-controlled within 2 weeks, consider referral to a specialist and go to scenario (B). 	
 • Continue copanlisib at the current dose.
(Scenario B)	
 • Asymptomatic SBP \geq 160 mmHg, or DBP \geq 100 mmHg, OR • Failure to achieve well-controlled BP within 2 weeks in Scenario A. 	
 • Adjust current or initiate new antihypertensive medication(s). • Titrate antihypertensive medication(s) during the next 2 weeks to achieve well-controlled BP. 	
 • Interrupt copanlisib. • Once BP is well-controlled, restart copanlisib at a reduced dose.
(Scenario C)	
 • Symptomatic hypertension OR • Persistent SBP \geq 160 mmHg, or DBP \geq 100 mmHg, despite antihypertensive medication and dose reduction of study treatment 	
 • Adjust current or initiate new antihypertensive medication(s). • Titrate antihypertensive medication(s) during the next 2 weeks to achieve well-controlled BP. • Referral to a specialist for further evaluation and follow-up is recommended. • Continue follow-up per protocol. 	
 • Discontinue copanlisib
(Scenario D)	
 • Refractory hypertension unresponsive to above interventions or hypertensive crisis. 	
 • Continue follow-up per protocol. 	
 • Discontinue copanlisib.

Non-infectious pneumonitis

The investigator is requested to differentiate between non-infectious pneumonitis, and infectious pneumonitis (viral, bacterial, or fungal), aspiration pneumonitis, or other pneumonitis clearly not due to a potential hypersensitivity reaction to the copanlisib infusion; and provide the basis for his/her assessment that it is infectious or other, as appropriate. The investigator is requested to report with the most specific clinical terms to describe the condition, not simple “pneumonitis”.

In the event of suspected non-infectious pneumonitis, modify copanlisib treatment as per table below.

Dose adjustment for non-infectious pneumonitis

Suspected or confirmed NIP per CTCAE	Action Taken	Re-treatment dose after recovery
Grade 1	No Change	NA
Grade 2	Dose Interruption Until recovery to \leq grade 1	Decrease dose to the next lowest dose level ^a
Grade 2 second re-occurrence	Permanent Discontinuation	NA
Grade 3	Permanent Discontinuation	NA
Grade 4	Permanent Discontinuation	NA

NA = Not applicable; NIP = Non-infectious pneumonitis; CTCAE = Common Terminology Criteria for Adverse Events.

a: Not applicable for 45 mg dose level. No re-escalation is allowed after the dose reduction.

Rev. Add16

The lowest dose level for patients with non-infectious pneumonitis is 45 mg; if a patient is already on the 45 mg dose level and cannot tolerate treatment study treatment will be discontinued permanently.

Rev. Add16

Dose modifications for Hematological Toxicities

Day	ANC		Platelets	Dose modifications
Day 1	$\geq 500/\mu\text{L}$	AND	$\geq 75,000/\mu\text{L}$	Treat at current dose level
	$< 500/\mu\text{L}$	OR	$< 75,000/\mu\text{L}$	Delay until count recovery

Use of WBC growth factors is allowed as per institutional guidelines for treatment or prevention of complication. Use of WBC growth factors to maintain dose intensity is not allowed.

Dose Modifications for General Non-hematologic Toxicities

This section does not refer to those non-hematologic toxicities for which dose modifications are listed above.

Grade	Action and Dose Modification
Grade 1 or transient Grade 2	No intervention
Grade 2 lasting \geq 7 days with optimal/best supportive care	Hold Copanlisib Resume at 60 mg after recovery to \leq grade 1 Recurrence at 60 mg: Hold Copanlisib Resume at 45 mg after recovery to \leq grade 1 Recurrence at 45 mg: Hold Copanlisib Resume at 30 mg after recovery to \leq grade 1 Recurrence at 30 mg: Discontinue Copanlisib
Grade 3	Hold Copanlisib Resume at 45 mg after recovery to \leq grade 1 Recurrence at 45 mg: Hold Copanlisib Resume at 30 mg after recovery to \leq grade 1 Recurrence at 30 mg: Discontinue Copanlisib
Grade 4	Discontinue treatment

Copanlisib will be discontinued if treatment delay is $>$ 4 weeks

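### The general non-hematologic table in Section 3.5 names fixed resume doses that fit only a patient still at 60 mg; for a patient already reduced, they conflict with the section's own reduction rules

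*Protocol*

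**What the plan says.** Table 1 in Protocol Section 3.5 sets dose levels of 60, 45 and 30 mg. The text around it gives three rules, none with an exception:

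- After an interruption for high-grade toxicity: "If there is need to interrupt dosing for grade 3/4 toxicity, then there will be a dose reduction as per the table below".
- At 30 mg: "if there is an indication for further dose reduction, the patient must permanently discontinue copanlisib".
- Re-escalation: "Dose re-escalation is not allowed after a dose reduction".

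The table for general non-hematologic toxicities, at the end of the section, covers events that have no rules of their own. Its row for grade 2 lasting at least 7 days starts "Hold Copanlisib Resume at 60 mg after recovery to" grade 1 or lower, and its grade 3 row starts "Hold Copanlisib Resume at 45 mg after recovery to" grade 1 or lower. The lower steps are written only as recurrences at a named dose, ending with "Recurrence at 30 mg: Discontinue Copanlisib".

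The toxicity-specific rules for grade 3 rash, hypertension (Scenario B) and grade 2 non-infectious pneumonitis are worded relative to the dose the patient is on. For grade 2 pneumonitis the instruction is "Decrease dose to the next lowest dose level", with the footnote "No re-escalation is allowed after the dose reduction" and a floor of 45 mg.

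For transient post-infusion hyperglycemia, a separate bullet permits re-escalation once glucose is controlled in the investigator's judgment.

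**The concern.** The fixed doses assume that every patient who meets the general table is still at 60 mg. The protocol makes other patients foreseeable. Someone reduced for hyperglycemia, rash, hypertension or pneumonitis under those rules can later have a first general event. The general table can also produce the case alone: grade 3 diarrhea takes the dose from 60 to 45 mg, and a first episode of prolonged grade 2 fatigue then points to the row that says 60 mg.

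The toxicities involved are not rare. Section 1.3 reports grade 3 hyperglycemia in 33.3% and grade 3 hypertension in 19.3% of 57 patients in the first-in-human study. Section 3.4 lists diarrhea, nausea and fatigue as likely (above 20%), and Section 3.5 has no separate table for any of these three. None of these figures is a dose-reduction rate at 60 mg.

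At stake are patient safety and uniform dosing. A site that follows the row as printed raises the dose, or fails to lower it, in a patient who has already needed less drug. No sample size or other stated statistical figure is affected.

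**Working it through.** **Inputs.** Dose levels 60, 45 and 30 mg (Section 3.5, Table 1). Three infusions per 28-day cycle, on Days 1, 8 and 15 (Section 3.1). Literal resume dose after a first general event: 60 mg for prolonged grade 2 and 45 mg for grade 3 (Section 3.5, general non-hematologic table).

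**Comparator from the Table 1 rules.** Prolonged grade 2: no more than the current dose, because re-escalation is banned. Grade 3 with interruption: one level lower (60 to 45, 45 to 30), and discontinuation from 30 mg.

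**Dose per cycle** = 3 × dose per infusion: 3 × 60 = 180 mg, 3 × 45 = 135 mg, 3 × 30 = 90 mg. Excess = literal dose ÷ allowed dose − 1.

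| Current dose | First general event | Table says | Table 1 rules allow | Per cycle | Result |
|---|---|---|---|---|---|
| 60 mg | Prolonged grade 2 | 60 mg | 60 mg | 180 vs 180 mg | Agrees |
| 60 mg | Grade 3 | 45 mg | 45 mg | 135 vs 135 mg | Agrees |
| 45 mg | Prolonged grade 2 | 60 mg | at most 45 mg | 180 vs 135 mg | 180/135 = 1.33, +33%; banned re-escalation |
| 45 mg | Grade 3 | 45 mg | 30 mg | 135 vs 90 mg | 135/90 = 1.50, +50%; required reduction not made |
| 30 mg | Prolonged grade 2 | 60 mg | at most 30 mg | 180 vs 90 mg | 180/90 = 2.00, +100%; banned, two levels up |
| 30 mg | Grade 3 | 45 mg | discontinue | 135 mg vs none | Treatment continues, at a higher dose, where it must stop |

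The two texts agree in both cases at 60 mg and conflict in all four at a reduced dose: three break the re-escalation ban and one omits the mandatory reduction. For a patient with pneumonitis at 45 mg, the 45 mg floor rules out the 30 mg step, so in the 45 mg grade 3 case a further reduction would mean stopping.

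**Where the table works.** For recurrences of the same event in a patient who starts at 60 mg, the ladder 60, 45, 30, discontinue is coherent. The gap is confined to a first general event at a reduced dose.

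**Hyperglycemia.** The ban under Table 1 and the later permission to re-escalate stand without a cross-reference. Table 2 lets a patient suspended for asymptomatic grade 3 hyperglycemia resume at the same dose once at grade 2 or lower, after discussion with the Study Principal Investigator. The general rule asks for a reduction, at grade 1 or baseline. In both places a site that takes the stricter option satisfies both texts, and the pre-dose glucose limit in Section 3.1 applies either way. The permission is therefore unclear, but no site is forced to break a rule.

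**The case against.** The strongest reply is that the Table 1 rules govern the whole of Section 3.5 and already settle the matter. Read with the ban, the 60 mg instruction can only concern a patient who has not been reduced; the next step, a recurrence at 60 mg, assumes that same patient. The mandatory-reduction sentence covers grade 3 at 45 mg, and the discontinuation rule covers grade 3 at 30 mg. No literal dose exceeds the 60 mg starting dose, and every resumption waits for recovery to grade 1 or lower.

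Much of this stands. A careful site has a safe ceiling, so the percentages above are not expected dosing errors. But the ceiling does not correct the row, which still prints a dose that the patient may not receive. For prolonged grade 2 it sets a maximum without naming the dose to resume. Treating a first event at 45 mg as a recurrence at 45 mg would supply a step, but the table does not say that.

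A reader might also infer that specific rules override general ones and that a sentence to that effect would cure everything. This document states no such principle, and the MATCH Master Protocol is not at hand. Applied to the general table, it would send a 45 mg patient back to 60 mg, even one whose pneumonitis rule bans re-escalation. For hyperglycemia it would choose the looser rule, which is a clinical decision. It would also leave hypertension unsettled: Scenario B restarts at a reduced dose, whereas Appendix IV makes reduction discretionary after an infusion interrupted for grade 3.

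The post-infusion hyperglycemia permission sits under its own heading and reads naturally as an exception. That is a fair reading, so only a clarifying cross-reference is called for.

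**Conclusion.** The general non-hematologic table is wrong as written for a patient already at 45 or 30 mg who has a first general event: its instruction conflicts with the Table 1 rules in four of four such cases, and in none of the two at 60 mg. The literal excess is 33%, 50% or 100% per cycle in three cases; in the fourth, the patient goes on at 135 mg per cycle instead of stopping.

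These sizes assume that a site follows the row and overlooks the Table 1 rules, and that all three infusions of the cycle are given. A reader might infer that the protocol will cause patients to be dosed at up to twice the intended level. The documents do not support that: the ban is explicit, the four cases are combinations of dose and grade rather than patients, and the number affected cannot be estimated from the protocol.

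A reader might also infer that the hyperglycemia rules cannot be followed together. They can, by taking the stricter option, so that part is a secondary matter of clarity. The main point should be fixed because it concerns safety and the remedy is simple.

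**What to change.** Reword the general non-hematologic table relative to the current dose:

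- First grade 2 event lasting at least 7 days: hold, then resume at the current dose after recovery to grade 1 or lower. On each recurrence, resume one level lower; discontinue on recurrence at 30 mg.
- Grade 3: hold, then resume one level lower after recovery to grade 1 or lower; discontinue if already at 30 mg.
- Keep the 45 mg floor for patients with non-infectious pneumonitis.

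The grade 4 row and the hematologic table need no change.

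Secondary: add a cross-reference to the re-escalation ban saying whether re-escalation after post-infusion hyperglycemia is an exception to it. The clinical team decides which way, and also decides between Table 2 and the general grade 3/4 rule for asymptomatic grade 3 hyperglycemia. Do not add a blanket statement that toxicity-specific tables prevail.

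The cost is amendment wording only; sample size and study procedures are unchanged.

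### Table 2's last row allows copanlisib to resume after any controlled grade 4 hyperglycemia, without excepting the post-infusion life-threatening events that section 3.5 says must end treatment

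*Protocol*

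**What the plan says.** Two blocks in Protocol section 3.5 deal with hyperglycemia.

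The first is headed "Dose Modification rules for transient post-infusion hyperglycemia". Its last bullet reads: "Occurrence of post infusion life-threatening copanlisib related hyperglycemia requires permanent discontinuation of the study drug". Its first bullet allows further dose reduction only while no discontinuation criterion has been met.

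The second, on management of hyperglycemia, follows directly and leads to Table 2. It is introduced by "Management guidelines for fasting patients with hyperglycemia are listed below in Table 2", and the table's footnote says "Based on fasting glucose level". The last row covers "3, symptomatic (e.g., blurred vision, frequent urination, excessive thirst) or grade 4". It suspends copanlisib until the event is grade 2 or lower. Its only stop condition is "The patient will be discontinued from the study if such therapy fails to control their hyperglycemia". After that it says "Dosing with copanlisib may otherwise resume at one dose level lower as outlined in Table 1".

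Neither the row nor the footnote mentions the post-infusion stop.

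**The concern.** The two blocks use different tests for whether a patient may be treated again. In the post-infusion list, a life-threatening event ends treatment. In the Table 2 row, the test is whether glucose-lowering therapy works; a grade 4 event that responds may be followed by more copanlisib at a lower dose. If one event falls under both blocks, one forbids what the other permits.

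The stake is patient safety. Sites tend to use a dose table by finding the row that matches the event. A site doing so here would find written permission to re-expose a patient after an event that the preceding list says must end treatment.

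**Working it through.** No arithmetic applies. The check compares the two rules and then looks for any text that settles the order between them.

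**1. The rules side by side**

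| | Post-infusion list, section 3.5 | Table 2, last row |
|---|---|---|
| Event | Post-infusion, life-threatening, related to copanlisib | Symptomatic grade 3, or any grade 4 |
| Stated setting | Transient, after infusion | Fasting glucose |
| Action | Permanent stop, no exception | Suspend; resume one level lower if controlled and grade 2 or below |
| Force | Mandatory | Permissive |
| Reference to the other rule | None | None |

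**2. Can one event fall under both?** The settings are named differently, but nothing makes them exclusive.
- Section 5.1.11 says hyperglycemia often lasts about 1 to 3 days after dosing, so a post-infusion rise can still be present when a fasting value is taken.
- The text introducing Table 2 is not confined to days away from infusion. On insulin it says "It should not be used to lower glucose level on the day of infusion due to the risk of hypoglycemia".

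Overlap is therefore possible. The protocol does not show how often it occurs.

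**3. Does other text correct the row?**
- Appendix III, the infusion-day glucose guidance, has no stop or resume rule.
- The general non-hematologic table in section 3.5 discontinues at grade 4, but it excludes toxicities that have their own rules, and hyperglycemia is one of them.
- Section 3.7 ends treatment for unacceptable toxicity, which is a judgement.
- The text around Table 1 narrows the permission. Treatment ends if the hold exceeds 4 weeks, or if a reduction is needed from 30 mg. The row's permission therefore matters for patients at 60 mg or 45 mg who recover within 4 weeks.

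**4. Does other text indicate which rule prevails?** Yes, indirectly. The first bullet of the post-infusion list makes further reduction conditional on no discontinuation criterion being met. Every event in the overlap is post-infusion, so that list applies to it, and Table 2 resumes only at a reduced dose. This places the stop above the reduction. The condition is not carried into Table 2.

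**5. Comparison within the protocol.** Grade 4 rash (Table 3), grade 4 hypertension (section 3.5 and Appendix IV), grade 4 non-infectious pneumonitis and other grade 4 non-hematologic toxicities all carry an explicit permanent stop. Among these, Table 2 alone allows resumption after grade 4, so the missing exception is easy to overlook.

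**The case against.** The strongest reply is that both rules can be obeyed. The stop is mandatory, while the table only says that dosing may resume and presents itself as guidance. A permission does not cancel a specific mandatory stop a few lines above it, and stopping satisfies both. The scopes are labelled separately, and the bullet on further dose reduction already ranks stop criteria above reduction. For harm to follow, a site would have to use the row and overlook the preceding list.

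Most of this stands. It shows what is intended and makes the point minor. It does not put the exception into the row that a site would consult, and that row, read alone, permits what the list forbids.

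A reader might go further in three ways that the protocol does not support:
- **That the rules contradict each other for every grade 4 event.** They do not. The stop is limited to post-infusion, drug-related, life-threatening events, and Table 2 to fasting values. Outside the overlap, resuming after a controlled grade 4 event is a choice the protocol makes openly.
- **That nothing indicates which rule governs.** The mandatory wording and the bullet on further reduction both point to the stop.
- **That the 33.3% grade 3 hyperglycemia rate in section 1.3 sizes the problem.** It is a grade 3 rate in 57 patients of a study that used weight-based doses. It says nothing about grade 4 or life-threatening events and should not be used as a magnitude.

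**Conclusion.** The point holds in a narrow form. Table 2's last row is wrong as written for one class of event: post-infusion, life-threatening, copanlisib-related hyperglycemia that is also graded 4 on fasting glucose. For that class it permits resumption where the post-infusion list requires a permanent stop. The protocol's other wording shows that the stop is meant to prevail, but the row neither repeats it nor points to it.

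Severity is minor. The protocol gives no rate of grade 4 or life-threatening hyperglycemia, so the frequency is unknown; it is probably low. No endpoint, sample size or analysis is affected.

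The conclusion rests on two assumptions: that a post-infusion event can be graded on a fasting value, which the 1 to 3 day persistence makes plausible; and that a life-threatening event can be graded 4. The protocol grades by CTCAE version 5.0 without printing the definitions, so how closely the two terms match cannot be checked from the document. The point needs only that they can coincide.

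**What to change.** Add one sentence to the dose-adjustment cell of Table 2's last row: *Post-infusion life-threatening copanlisib-related hyperglycemia: permanently discontinue copanlisib; the post-infusion discontinuation criteria above override this table.* Leave the resumption rule for other symptomatic grade 3 or grade 4 events as it is.

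The cost is one sentence at the next amendment, with no effect on patient numbers or analysis.
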